6.2.1 Definition of secondary estimand 1: Complete renal remission (CRR)

- Population: moderately active proliferative lupus nephritis
- Variable: CRR at post dose timepoints
- Treatment: CFZ+SOC, Placebo+SOC
- Measure of intervention effect: Proportion of CFZ533 patients with CRR at post dose timepoints

CRR at a timepoint is defined as having UPCR ≤ 0.2 mg/mg as well as eGFR within 25% of baseline value and normal urine sediment. If a subject died, received rescue medication or discontinued from treatment then they will be analyzed as not having CRR from the timepoint of the event. CRR status will be assessed using first morning void if available and if not then using the clinic spot sample.

Analysis

The proportion of patients fulfilling the definition of complete renal remission will be summarized by treatment and visit and displayed graphically in barcharts.

Composite strategy will be used to deal with death, rescue medication and treatment discontinuation inter-current events. If a subject died, received rescue medication or discontinued from treatment then they will be analyzed as not having CRR.

No other inter-current events will be taken into account in the estimand.

Additional analyses will be performed considering the first morning void and clinic spot samples separately.

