6.1.1 Definition of primary estimand 1: UPCR

- Population: moderately active proliferative lupus nephritis patients.
- Variable: Ratio from baseline in UPCR at Week 25
- Treatment: CFZ+SOC, Placebo+SOC
- Summary Measure: Ratio of Geometric Means of CFZ533 versus placebo.

Hypothetical strategy will be used to deal with death, rescue medication and treatment discontinuation inter-current events. Data from patients taking rescue medication during the trial (or failing to tolerate steroid taper, for patients receiving oral corticosteroid at baseline) will be excluded from the date of rescue medication intake or failure of the steroid taper. Data from patients who discontinue study treatment will also be excluded, from the date of study drug discontinuation. A medical assessment prior to database lock will determine which patients are deemed to have failed the steroid taper based on clinical relevance of the steroid dose taken and the potential impact on the primary endpoint.

No other inter-current events will be taken into account in the estimand.

Commercially Confidential Information

Statistical analysis model

The ratio from baseline in UPCR will be log transformed prior to the analysis. A repeated measures model will be fitted with factors for treatment group (CFZ533 or placebo) and visit (e.g. Week 5, 9, 13 etc.). The model will also include a factor for the prednisone dose-equivalent at baseline (≤ 10 mg, > 10 mg) based on the concomitant medication information in the database rather than the stratification factor from the randomization. Log-transformed baseline UPCR will be included in the model as a covariate along with the interactions between visit and all of the fixed effects and the log-transformed baseline by visit interaction. A normal errors model will be assumed with an unstructured covariance matrix to account for the correlation within subjects. The model will be estimated using maximum likelihood techniques. If there are values of 0 then 0.1 will be added to all the UPCR data prior to the log transformation.

At each of the visits, the difference between the CFZ533 and placebo group will be estimated (along with its corresponding 95% confidence interval) and then back-transformed to provide an estimate of the ratio between treatment groups.

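### CRR has no rule for steroid-taper failure, so a UPCR value that the primary analysis discards can still count towards a complete remission

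*SAP*

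**What the plan says.** **Primary estimand (SAP 6.1.1).** The named intercurrent events are death, rescue medication and treatment discontinuation, under a hypothetical strategy. The data rule that follows goes further: "Data from patients taking rescue medication during the trial (or failing to tolerate steroid taper, for patients receiving oral corticosteroid at baseline) will be excluded", and the exclusion runs "from the date of rescue medication intake or failure of the steroid taper". A medical assessment before database lock decides who failed the taper. Protocol 11.4.3 contains the same exclusion, also in parentheses after rescue, but mentions only the rescue date.

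**CRR (SAP 6.2.1).** The strategy is stated as: "Composite strategy will be used to deal with death, rescue medication and treatment discontinuation inter-current events". The non-remission rule is: "If a subject died, received rescue medication or discontinued from treatment then they will be analyzed as not having CRR". It appears twice with the same three triggers; the first statement adds that it applies from the time of the event. The section then says: "No other inter-current events will be taken into account in the estimand". The remission criteria are UPCR at or below 0.2 mg/mg "as well as eGFR within 25% of baseline value and normal urine sediment". Neither SAP 6.2.1 nor protocol 11.5.1.3 sets a condition on steroid dose.

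**Other relevant text.** SAP 6.1.1 has two separate triggers at more than 15% of patients: one for rescue or discontinuation, and one for taper failure, which leads to a supportive time-to-event analysis. Neither is set out for CRR. Protocol 6.10 ties rescue to starting or increasing standard-of-care therapy for a severe flare.

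**The concern.** The two efficacy estimands in SAP Table 6-1 use the same UPCR measurements, with the same fallback from first morning void to clinic spot sample. For one of them, the sponsor judged that values after taper failure should not be used. The pre-lock assessment rests on the clinical relevance of the steroid dose taken and on its likely effect on the primary endpoint. UPCR is that endpoint and is also a component of CRR, yet the CRR rule says nothing about taper failure.

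What is at stake is the reading of the only secondary endpoint with its own estimand. In a placebo arm of about 20, a few patients visibly change the planned bar charts. Programmers could also derive different CRR rates, depending on whether they treat taper failure as a form of rescue.

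**Working it through.** **1. The plan's own figures.** No figure is stated for CRR: protocol 11.8 marks power for key secondary variables as not applicable. The arm sizes come from protocol 11.7.
- Inputs: 34 and 17 completers, SD 0.7 (taken as log scale), true ratio 0.64, one-sided 10% level, observed ratio at most 0.80.
- SE = 0.7 × √(1/34 + 1/17) = 0.208. True log difference = ln 0.64 = −0.446.
- Significance threshold = 1.2816 × 0.208 = 0.266. This is stricter than 0.223, so it decides the joint criterion.
- Power = Φ((0.446 − 0.266)/0.208) = 0.806, against about 80% stated.
- Enrolment = 51/0.85 = 60, that is 40 and 20.

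The stated design reproduces. Nothing in this point changes it.

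**2. The same patient under both rules.** Take a patient on oral corticosteroid at baseline who is deemed to have failed the taper, takes no rescue and continues study drug.

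| | Primary UPCR (SAP 6.1.1) | CRR (SAP 6.2.1) |
|---|---|---|
| Death, rescue, discontinuation | data excluded | not in CRR |
| Taper failure | data excluded from its date | not mentioned; list closed |
| Week 25 UPCR of this patient | discarded | used |

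If that UPCR is at or below 0.2 mg/mg and the eGFR and sediment criteria are met, the patient is a complete remission.

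**3. Effect per patient.** One patient is 1/40 = 2.5 points on CFZ533 or 1/20 = 5 points on placebo.

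**4. Illustrative range.** The rates below are assumptions; the documents give none. Let *f* be the share of an arm that fails the taper without rescue or discontinuation, and *r* the share of those who meet the CRR criteria. Counting them as not in CRR lowers the arm's proportion by *f* × *r*.
- Lowest case: 0.05 × 0.10 = 0.5 points.
- Highest case: 0.30 × 0.50 = 15 points (6 of 40, or 3 of 20).

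With the same *r* in both arms, the difference CFZ533 − placebo moves by *r* × (*f* placebo − *f* CFZ533):

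| *f* CFZ533 | *f* placebo | Shift for *r* = 10% to 50% |
|---|---|---|
| equal | equal | 0 |
| 5% | 30% | +2.5 to +12.5 points |
| 15% | 30% | +1.5 to +7.5 points |
| 30% | 15% | −1.5 to −7.5 points |

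The sign depends entirely on which arm has more such patients.

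**The case against.** **Taper failure may be meant as a form of rescue.** SAP 6.1.1 formally names the same three events as SAP 6.2.1 and ends with the same closing sentence. Taper failure stands only in parentheses after rescue, and protocol 11.4.3 gives both a single date. If it is rescue, SAP 6.2.1 already covers it. This stands in part: one cannot say that the primary estimand formally lists taper failure as an intercurrent event. But the SAP gives it its own date, its own medical assessment and its own 15% trigger, and a patient merely kept above the scheduled dose does not fit the description of rescue in protocol 6.10. If the sponsor does mean rescue, SAP 6.2.1 should say so.

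**Redaction.** Text after the event rules in SAP 6.1.1 and in protocol 3.1 and 11.4.5 is blacked out, and a linking definition could sit there. That cannot be excluded. The closed list in SAP 6.2.1 is nevertheless legible.

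**Steroid-driven remission.** A reader might infer that extra steroid produces these remissions. The documents do not show it. A steroid increase for a severe flare is already rescue. A patient kept on the baseline dose entered with UPCR of at least 0.5 mg/mg on a dose stable for at least two weeks, so crediting that dose with a later remission is speculative.

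**Expected frequency.** A reader might also take the 15% figure as a forecast of at least 10 failures among 60. It is a conditional trigger, and it counts taper failures, not failures who also meet all the CRR criteria.

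**Different strategies are legitimate.** This is true: hypothetical for UPCR and composite for CRR is a fair choice, and the protocol's ACR-based definition has no steroid condition. But a difference in strategy does not explain why one event drops out without comment.

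**Follow-up visits.** After Visit 201, SAP Table 1-1 leaves steroid use to need for every patient, and the pre-lock assessment is framed around the primary endpoint. Carrying non-remission past that visit would be hard to defend. This stands, and it limits the fix.

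**Conclusion.** The gap is real but modest. As written, a taper failure without rescue who remains on study drug can count as a complete remission on a UPCR value that the primary analysis excludes. The two rules are out of step in how they handle data; this is not a formal contradiction between two lists of intercurrent events.

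The only firm size is 2.5 points per CFZ533 patient and 5 points per placebo patient, given 40 and 20 randomized. The range of 0.5 to 15 points per arm rests on assumed rates. A reader might infer bias towards no effect; that needs more such patients on placebo, and no rates by arm are given. The difference could equally widen or stay put.

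CRR is summarized by treatment and visit, with no planned test or power claim. Concomitant therapies are listed by subject, so individual cases can be traced. The primary conclusion is unaffected. The change is worth making because it is cheap and removes a choice that would otherwise be left to programming.

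**What to change.** In SAP 6.2.1:
- Analyse patients deemed taper failures by the pre-lock assessment in SAP 6.1.1 as not in CRR from the date of taper failure through Week 25.
- Present CRR without this rule as a sensitivity summary, so that the protocol's steroid-free definition remains visible.
- State separately how CRR is handled at visits after Visit 201.

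The taper-failure flag and date are already needed for the primary analysis. The cost is SAP wording before database lock, one additional summary and a possibly slightly lower CRR proportion. No new data are needed, and sample size and steroid management do not change.

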6.2.2 Other secondary PD variables

For other secondary PD variables (UACR, total soluble CD40 in plasma, hematuria and cellular casts) data will be listed together with changes from baseline (ratio to baseline for UACR and total soluble CD40 in plasma) by treatment, subject, and visit/sampling time point. For hematuria and cellular cast data only positive results are reported therefore if a result was negative at baseline the baseline value will be imputed as 0.

Descriptive summary statistics will be provided by treatment and visit/sampling time point. Summary statistics will include mean, SD, CV, median, minimum and maximum. Geometric statistics will also be presented for UACR and total soluble CD40 in plasma. Mean (SD) profile plots (geometric mean and SE for UACR and total soluble CD40 in plasma) will be generated. For UACR outputs will be separated out by first morning void separately, clinic spot sample separately and using first morning void if available and if not then using the clinic spot sample.

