2.2 Secondary objective(s)

Secondary objective(s)	Endpoints related to secondary objective(s)

• To assess the effect of CFZ533 on relevant renal outcomes at different time points• To evaluate the pharmacokinetics (PK) and pharmacodynamics (PD) of CFZ533 in LN patients, after multiple 10 mg/kg IV doses• To evaluate the immunogenicity of CFZ533 in LN patients, after multiple 10 mg/kg IV doses	
• Ratio from baseline in the following parameters:
○ UPCR (first morning void)○ hematuria and cellular casts• Proportion of patients who fulfill the criteria for complete renal remission (CRR) according to ACR recommendation (Wofsy et al 2012)• PK: Free CFZ533 concentrations in plasma.• Parameters (free CFZ533): C_{trough,ss} or C_{min,ss}, C_{max,ss}, and AUC_{last} (after last dose)• PD: Total soluble CD40 concentrations in plasma: pre-dose, during treatment and follow up. Rate, extent and duration of target engagement.• Anti-CFZ533 antibodies in plasma: baseline, during treatment and follow-up, incidence of ADA-positive patients

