4.1 Inclusion criteria

Population eligible for inclusion in this study must fulfill **all** of the following criteria:

1. Understand the study procedures and provide written informed consent before any study-related assessment is performed.
2. Men and women with systemic lupus erythematosus (see below), aged ≥ 18 years and ≤ 75 years at screening, fulfilling at least 4 out of 11 criteria for SLE as defined by the American College of Rheumatology ([Tan et al 1982](#), revised by [Hochberg 1997](#)).

3. Subjects must have a body mass index (BMI) within the range of 18 - 40 kg/m². (BMI = Body weight (kg) / [Height (m)]²) to participate in the study at Screening visit.
4. Histological diagnosis of proliferative lupus nephritis World Health Organization (WHO) ISN/RPS ([Weening et al 2004](#)) Class III or IV within 5 years of screening.
5. Presence of antinuclear autoantibody (ANA titer \geq 1:80 at screening)
6. First morning void or spot urine UPCR \geq 0.5 mg/mg (56.52 mg/mmol) at Screening visit and Baseline visit
7. At least one of the following at Screening visit:
 - a. low complement level (C3 $<$ 0.9 g/L or C4 $<$ 0.1 g/L), and/or
 - b. elevated anti-dsDNA (\geq 30 IU/mL), and/or
 - c. urine sediment consistent with active proliferative lupus nephritis such as presence of cellular (granular or red blood cell) casts or hematuria ($>$ 5 red blood cells per high power field) if other causes such as menstrual bleeding are excluded
8. Patient must have sufficient kidney function as estimated by eGFR $>$ 30 mL/min/1.73m² at screening and baseline visits
9. Patients must have active disease as defined by proteinuria and additional symptoms as defined above (criterion 7) despite standard of care therapy for lupus nephritis as considered appropriate by the treating physician (e.g., corticosteroids and/or immunosuppressive or immunomodulatory treatments such as mycophenolate, azathioprine, methotrexate or hydroxychloroquine). For guidance, see published guidelines such as by [Bertsias et al 2012](#) and [Hahn et al 2012](#)
10. If the patient is taking oral corticosteroid treatment at screening, the dose (max. 30 mg prednisone or equivalent per day) must be stable for at least 2 weeks prior to randomization

Commercially Confidential Information

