8.1 Assessment schedule

Subjects should be seen for all visits/assessments as outlined in the assessment schedule or as close to the designated day/time as possible.

Missed or rescheduled visits should not lead to automatic discontinuation. Subjects who prematurely discontinue the study drug for any reason should be continuing their study participation, i.e., to complete all study visits.

If an epidemic or pandemic (e.g. COVID-19 pandemic) limits or prevents on-site study visits, alternative methods of providing continuing care may be implemented. Phone calls, virtual contacts (e.g. teleconsult) or visits by site staff to the participant's home depending on local regulations and capabilities, can replace on-site study visits, for the duration of the pandemic until it is safe for the participant to visit the site again.

Table 8-1 Assessment schedule

Epoch	Screening		Treatment								Follow Up					
Visit Name	SCR	BL	Treatment								Follow Up				EOS	
Visit Numbers	1	2	101	102	103	104	105	106	199	201	202	203	204	205	206	299
Week	-4 to -1		1	3	5	9	13	17	21	25	29	33	37	41	45	49
Day	-28 to -8	-7 to -3	1	15 ±1	29 ±2	57 ±2	85 ±2	113 ±2	141 ±2	169 ±3	197 ±3	225 ±3	253 ±3	281 ±3	309 ±3	337 +3
Pre/Post ¹			Pre	Post	Pre	Post	Pre	Post	Pre	Post	Pre	Post	Pre	Post		
Informed consent	X															
Genetic consent	X															
Eligibility criteria	X	X														
Medical history/current conditions	X															
Demography	X															
Body height	X															
Body weight	X	X	X	X	X	X	X	X	X	X	X	X	X	X	X	X
Body temperature	X	X	X	X	X	X	X	X	X	X	X	X	X	X	X	X
Blood pressure/pulse rate	X	X	X	X	X	X	X	X	X	X	X	X	X	X	X	X
Physical examination	X	X	X	X	X	X	X	X	X	X	X	X	X	X	X	X
Electrocardiogram	X	X	X	X	X	X	X	X	X	X	X	X	X	X	X	X

Commercially Confidential Information

Hematology/Clinical Chemistry/ Urinanalysis ⁹	X	X	X	X	X	X	X	X	X	X	X	X	X	X	X	X
Hepatitis, CMV, HIV screen	X ²		X ⁸		X ⁸											
TB screen	X															
FSH ³	X															
Pregnancy test ³	X	X	X	X	X	X	X	X	X	X	X	X	X	X	X	X
ESR, CRP	X	X		X	X	X	X	X	X	X	X	X	X	X	X	X
IgG, IgM	X	X			X			X				X		X		X
C3, C4 Complement	X	X			X			X				X		X		X
Lupus anticoagulant	X		X								X					X
Coagulation test	X	X		X	X	X	X	X	X	X	X	X	X	X	X	X
PK collection ¹			X	X		X	X		X	X	X	X	X	X	X	X
PD collection (total soluble CD40)			X		X				X				X		X	X
Immunogenicity			X		X			X		X		X		X		X

Commercially Confidential Information

Drug administration		X	X	X	X	X	X	X	X							
Study completion																X

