11.5.1.2 UPCR, hematuria and cellular casts

First morning void and clinic spot urine sample UPCR, hematuria and cellular casts will be listed by treatment, subject and visit/sampling time-point. Descriptive statistics will be provided by treatment and visit/sampling time.

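### SAP 6.2.2 gives negative hematuria and cast results a value at baseline only, so patients who clear drop out of the later by-visit summaries

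*SAP*

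**What the plan says.** Protocol 2.2 lists hematuria and cellular casts among the secondary endpoints, under "Ratio from baseline in the following parameters". Protocol 11.5.1.2 adds only that UPCR and "hematuria and cellular casts will be listed by treatment, subject and visit/sampling time-point", with descriptive statistics by treatment and visit. It gives no value for a negative result.

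SAP 6.2.2 supplies the handling rule. It works with changes from baseline for these two variables, then states that for them "only positive results are reported therefore if a result was negative at baseline the baseline value will be imputed as 0". It gives no value for a negative at any later visit. For the outputs by treatment and visit it says "Summary statistics will include mean, SD, CV, median, minimum and maximum", and "Mean (SD) profile plots (geometric mean and SE for UACR and total soluble CD40 in plasma) will be generated".

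Two further places bear on the point. Inclusion criterion 7 in protocol 4.1 asks for "At least one of the following at Screening visit" and offers active urine sediment as one of three alternatives, so patients with negative sediment can be enrolled. The row "Hematology/Clinical Chemistry/ Urinanalysis" in protocol Table 8-1 recurs through treatment and follow-up, so the question of what a later negative means arises repeatedly.

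**The concern.** The SAP's reason for imputing (negatives leave no record) holds at every visit, but its imputation stops at baseline. The baseline and later summaries then describe different groups of patients: everyone at baseline, and only those currently positive afterwards.

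This has two consequences. A patient whose hematuria or casts resolve, which is the improvement the secondary objective is looking for, contributes nothing after baseline. And a profile plot can climb from its first point with no patient having changed. No test is visibly planned for these variables, so the tables and plots are the result a reader of the study report will see.

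**Working it through.** The documents state no figure on this point, so there is nothing to reproduce. The check is direct arithmetic.

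**Inputs.** Arm sizes of 40 and 20 are from protocol 11.7. Everything else is assumed, because the documents give no rates: p = share positive at baseline; m = 20 units in every positive patient; c = share of positives who clear; o = share of baseline-negatives who turn positive; f = proportional fall among those who stay positive.

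**1. Nobody changes, zeros entered in the baseline summary.** Baseline mean = p·m + (1 − p)·0 = p·m. Later mean = m, because only positives have a value. Ratio = 1/p, whatever m is.

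| p | Baseline mean | Later mean | Factor | Contributing after baseline (of 40 / of 20) |
|---|---|---|---|---|
| 40% | 8 | 20 | 2.5 | 16 / 8 |
| 60% | 12 | 20 | 1.67 | 24 / 12 |
| 80% | 16 | 20 | 1.25 | 32 / 16 |

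The mean change among contributors is 0 here, which is correct. The artefact is in the raw means and the plot.

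The factor 1/p is the rise that would be plotted. It equals the inflation over the true mean only if a negative is truly 0. If a negative were really 5 cells, the true mean at p = 60% would be 0.6·20 + 0.4·5 = 14, and the later mean would overstate it by 20/14 = 1.43.

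**2. Nobody changes, zeros used only to compute changes.** The raw mean is 20 at baseline and 20 later. There is no rise, but the mean describes positives only at every visit.

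**3. Changes when patients switch status.**

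- True mean change = m·[(1 − p)·o − p·c − p·(1 − c)·f]
- As written = m·[(1 − p)·o − p·(1 − c)·f] / [p·(1 − c) + (1 − p)·o]

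The clearing term p·c is absent from the second numerator. With f = 0 the as-written mean change cannot be negative, however many patients clear.

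Three illustrations, each within one arm of 40:

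- *Half of the positives clear* (p = 50%, c = 50%, o = 0, f = 0). Of 20 positives, 10 clear. The true mean falls from 10 to 10·20/40 = 5, a change of −5. As written, 10 patients contribute, the later mean is 20 and the mean change is 0.
- *Turnover at constant prevalence* (p = 50%, c = o = 20%, f = 0). Four clear and four newly turn positive. True change = (4·20 − 4·20)/40 = 0. As written = (16·0 + 4·20)/20 = +4.
- *Falling levels as well* (p = 60%, c = 20%, o = 5%, f = 40%). Of 24 positives, 4.8 clear and 19.2 fall by 8 units; 0.8 are new. True = (−96 − 153.6 + 16)/40 = −5.84. As written = (−153.6 + 16)/20 = −6.88.

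So changes may be understated or overstated. The direction is not fixed.

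**4. With 0 entered at every examined visit.** In step 1 the means stay at 8, 12 and 16. In the first illustration the mean falls from 10 to 5, as it should.

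**The case against.** The strongest reply is that the rise in the plotted mean depends on a reading. The imputation sentence directly follows the one on changes from baseline, so the zero may be meant only as a reference value for those changes. Raw means would then be positives-only throughout and the 1/p factor would not arise. This stands as a limit on the 1/p result. It does not rescue the rule: a patient who clears still has no later value and no change.

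The programmers may intend 0 at every visit. That is possible, but the sentence says baseline, and the fix would then only write down the intention.

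A rule may also sit elsewhere. Text is redacted between protocol 8.6.4.2 and 8.6.4.4 and after SAP 7.1, and SAP 1.1 refers to other RAP documents. How sediment is reported, and whether it is examined at every urinalysis visit, is not visible. This cannot be excluded, although SAP 6.2.2, where the rule is set, is visible.

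Complete renal remission requires normal urine sediment at each visit (protocol 11.5.1.3, SAP 6.2.1), so sediment status must be determined after baseline for that endpoint. This suggests that negatives can be identified, but it assigns no value to hematuria or casts in 6.2.2.

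A reader might also infer that the rule biases the treatment comparison, or even reverses its sign. The documents do not support that. SAP 6.2.2 plans no between-arm contrast for these variables, says only that their changes will be listed, and gives none of the rates from which a direction could be derived.

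**Conclusion.** The point holds as a defect in a descriptive derivation. Followed as written, SAP 6.2.2 leaves post-baseline negatives without a value and so drops patients who clear from the summaries of a named secondary endpoint. That is true under either reading of the imputation sentence.

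On the natural reading, the by-visit mean also rises by 1/p when nothing changes. Its size rests on the assumed p. Under the other reading the raw means need not rise, but changes are still distorted once patients switch status, by an amount and in a direction the documents do not determine.

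The reach is small: listings, by-visit summaries and profile plots. The study is exploratory, the primary UPCR analysis is unaffected, and these variables are not among the key estimands in SAP Table 6-1. Confidence is moderate because of the redactions.

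**What to change.** In SAP 6.2.2, replace the baseline-only rule with one for all visits: hematuria and casts take the value 0 at baseline and at every post-baseline visit where urine was examined and no positive result was reported; the value is missing only where no sample was examined.

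This needs a record that the test was performed, which the public text does not show. The sponsor should confirm that it exists; without it, a negative cannot be told from a missed sample. If it exists, the cost is one SAP sentence and the derivation code, with no change to data collection.

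Optionally, report the proportion positive by arm and visit beside the means, so that clearing is seen directly.
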